9.6 Recruitment Strategy

Sites will be recruiting potential study subjects from their population of primary total hip arthroplasties. Sites will provide screening/enrollment logs to the Sponsor so that the Sponsor can monitor progress and reallocate cohorts as needed. Sites will be instructed to begin actively recruiting all subjects upon receipt of the IRB approval letter. Screening results are documented on the screening and enrollment log.

9.7 Enrollment & Subject Identification Number

A study subject is **enrolled** when they have met eligibility criteria, been consented and had the THA procedure and study device implanted per protocol. Once enrolled, the site assigns the subject ID number which is comprised of a two-digit site code followed by a 4- digit subject specific code. For example, the first three enrolled subjects at site #06 would be: 06-0401, 06-0402, 06-0403.

9.8 Subject Evaluations and Follow-up

Diagnostic, demographic and operative information and clinical follow-up for each enrolled Subject will be documented on case report forms which have been developed specifically for this study. Examples of the case report forms for this post-approval study are provided in **Exhibit A**. The "Status" case report form (CRF) is completed for all subjects to identify which protocol each subject is participating. Details of subject evaluations are summarized in **Table 3** below.

9.9 Table 3 Subject Evaluations.

Table 3 Subject Evaluations	
Diagnostic, demographic & Study entry	Diagnostic, demographic and study entry criteria are documented on the Subject History case report form.
Clinical Assessment	The modified Harris Hip Evaluation will be used to clinically assess each subject at the pre-op and post-op intervals specified in the Table 4 below. Also note, range of motion (ROM) at the 6 Week follow-up interval is an optional assessment .
Subject Self-Assessment	Subjects will also complete hip outcomes self-assessment, which includes questions about their satisfaction and hip function starting at the 1 year post-op interval.
Radiographic	
High quality antero-posterior (AP) and lateral radiographs of the operative hip will be obtained during the same post-op follow-up intervals as for the clinical evaluations (i.e., 6 weeks, 1-5 years). Of note, for pre-op films only, the visit window can be -180 days before surgery.
 
An additional AP femur view is required only if the distal tip of the femoral stem cannot be seen and/or assessed on the AP view.
 
Also, at the first post-op visit, at 6 Weeks, a Cross-Table Lateral film will be collected to permit assessment of cup positioning. All original radiographs will be retained by the site and digital copies will be sent to the sponsor through a web-based application. Alternate methods to submit radiographs to sponsor must be pre-arranged. Analysis of the radiographs by an Independent Radiographic Reviewer (IRR) may involve the use of a web-based application. Observations will be documented by the IRR on to the radiographic CRFs and entered into the study database.

Risk Analysis (Safety)	See Section 10 .

Interim Visits	
An interim office visit is defined as any visit at the study site where a study Subject is seen by one of the site staff including the Principal Investigator (PI), any sub-investigator (as appropriate), and anyone identified on the PI's team, outside of the scheduled study visit. An interim visit is only to be reported when the visit falls between study intervals as described in Table 4. An Interim Visit CRF is not to be completed if the Subject comes in for additional, unplanned visits in the "in-window" study interval.
 
If the previous protocol-defined, study interval visit was missed, the required CRFs in that previously-missed interval visit are also required along with the Interim Visit CRF.
 
If the interim visit is related to a new, worsening, or resolved adverse event, both an Adverse Event CRF and Interim Visit CRF are completed.

End of Study/ Withdrawal	
This form must be completed for all enrolled subjects to either reflect
 
 • Completion of final endpoint (Minimum 5 years) • Premature withdrawal 
Study participation may be prematurely discontinued through revision of acetabular components (shell and/or liner), withdrawal of consent, or death.
 
➤ NOTE: A revision is defined as a surgical procedure of the affected hip where one or more of the THA components (femoral stem, femoral head, acetabular shell and/or acetabular liner) are removed. Of note, if both the acetabular shell and ceramic liner remain intact, the Subject will continue to be followed in the study.
 
➤ NOTE: Should it be necessary for the Subject to undergo a revision of either the acetabular shell and/or the acetabular liner between the date of the enrollment and the completion of the study data acquisition, the Subject is withdrawn from study participation. Thus, both an Adverse Event (AE) CRF and an END of Study/Withdrawal CRF would be completed.

Electronic Case Report Forms (CRFs) entered into an electronic data capture (EDC) system will be used to collect all Subject data once a Subject is enrolled in the study. Study sites will be instructed to enter Subject data on to the CRFs via the EDC web-based database portal.

The patient-reported outcome measure, CRF 4a, Subject Hip Outcomes (Clinic) will be recorded on a paper-based CRF. The data will then be entered into the respective CRF within the EDC system by the PI or designee. The patient-reported outcomes measure captured on paper-based CRFs must be stored in the Subject's medical notes, as these are considered to be the source document.

The study database has been validated in accordance with 21 CFR Part 11, European Commission's Directive on Data Protection and US Safe Harbor Certification. Prior to being released for importation of patient activity and study data, validation of the study level components will be conducted in accordance with approved user

acceptance testing procedures. Access to this system will be controlled so that only authorized users will have the ability to enter into the system. The system is considered a closed system according to 21 CFR Part 11 Electronic Records; Electronic Signatures. The Postoperative visit intervals will be assigned the following schedule:

9.10 Table 4: Postoperative Visit Intervals

One Event / Visit	6 Week	1 Year	2 Year	3 Year	4 Year	5 Year Min
	*1–92 d	275-455 d	640-820 d	1,005-1,185 d	1,370-1,550 d	1,825–2,555 d

*6-Week follow-up ROM is an **optional** assessment, based on standard of care procedures at each study site.

Follow-up of orthopaedic patients is known to be a challenge, particularly after the 2-year postoperative visit. Ideally, all subjects are to be seen in clinic at the intervals described in the above table so that they may be physically assessed, and radiographs obtained per this protocol. In order to optimize mid-term follow-up compliance, site personnel are permitted to contact the study subject in the 3- and 4-year intervals by phone (in place of a clinic visit) to assess the current status of the hip. For these limited circumstances, the site shall complete CRF 4b - Subject Hip Outcomes (Phone), which will provide information regarding survivorship and safety, in addition to patient satisfaction via direct data entry. In the event that a subject discloses a safety event, such as a hip problem, they should be encouraged to return to clinic for assessment.

10 RISK ANALYSIS

10.1 Potential Adverse Events (AEs)

Adverse Events (AEs) must be reported for all Subjects and AE determination will be done by the Principal Investigator, or appropriate designee.

Potential AEs include:

- Excessive wear of the ceramic components secondary to damage of mating wear surfaces or debris particles;
- Metal sensitivity reactions;
- Possible detachment of the coating(s) on the femoral stem or acetabular shell components, potentially leading to increased debris particles;
- Device related noise such as, clicking, popping, squeaking or grinding;
- Pain;
- Femoral or acetabular perforation, or bone fracture while seating the device;
- Damage to blood vessels resulting in hematoma;

- Temporary or permanent nerve damage resulting in pain or numbness of the affected limb;
- Undesirable shortening or lengthening of the limb;
- Traumatic arthrosis of the hip from intraoperative positioning of the extremity;
- Cardiovascular disorders including venous thrombosis, pulmonary embolism, or myocardial infarction;
- Temporary or permanent neuropathies;
- Delayed wound healing;
- Infection;
- Osteolysis;
- Fracture, migration, loosening, subluxation, or dislocation of the prosthesis or any of its components, any of which may require a second surgical intervention or revision;
- Periarticular calcification or ossification, with or without impediment to joint mobility;
- Inadequate range of motion due to improper selection or positioning of components, by femoral impingement, and periarticular calcification; and
- Death.

These possible AEs are not unique to the CERAMAX® Ceramic Hip System and, as stated above, may occur with any total joint replacement surgery.

10.2 Potential Adverse Events (AEs) Associated with the CERAMAX® Ceramic Hip System

The most commonly reported adverse events related to the DePuy Synthes CERAMAX® Ceramic Total Hip System are:

- Wear of the ceramic acetabular components has been reported following total hip replacement. Higher rates of wear may be initiated by particles of cement, metal, or other debris that can cause abrasion of the articulating surfaces. Higher rates of wear may shorten the useful life of the prosthesis, and lead to early revision surgery to replace the worn prosthetic components.
- While rare, fatigue fracture of the prosthetic component can occur as a result of improper assembly, trauma, strenuous activity, improper alignment, or duration of service.
- Component dissociation.
- Breakage or chipping of the ceramic femoral head and/or ceramic acetabular insert.

There are no additional risks to the subject associated with participation in this study. The evaluations included in the study are considered to be the standard of care for following total hip replacement patients. Likewise, there is no personal benefit to the subject for participation in this study. However, data collected in this study will contribute to the safety profile of this Ceramic on Ceramic articulation.

10.3 Table 5 Definitions of Adverse Events (AE) Types

For this protocol, the term “expected” will be synonymous with the term “anticipated” and “unexpected” will be synonymous with “unanticipated”.

This protocol requires each study site to report AEs, serious adverse events (SAEs), adverse device effects (ADEs), serious adverse device effects (SADEs), and unexpected (unanticipated) adverse device effects (UADEs) to their respective IRB/EC per their IRB/EC requirements.

Table 5 Definitions of Adverse Event (AE) Types	
Awareness (Date of AE Awareness)	The day, month and year that the study site becomes aware of information from any source that reasonably suggests that an AE has occurred. Note: This date may or may not correspond to the date of onset. The date of awareness is critical to reporting timelines.
Adverse Event (AE)	AE is defined as an untoward medical occurrence, unintended disease or injury, or untoward clinical signs (or change or worsening of a pre-existing medical condition) in a patient, which may or may not have an association with the device. AE is synonymous with “complication” or “medical event”.
Adverse Device Effect (ADE)	ADE is defined as an Adverse Event related to the use of an investigational medical device. Notes: This definition includes adverse events resulting from insufficient or inadequate instruction for use, deployment, implantation, installation or operation, or any malfunction of the medical device under study. This definition includes any event resulting from user error or from intentional misuse of the medical device under study.
Serious Adverse Device Effect (SADE)	SADE is defined as an Adverse Device Effect that has resulted in any of the consequences characteristic of a serious adverse event.
Serious Adverse Event (SAE)	SAE is defined as an Adverse event that: 
 • led to a death, • led to a serious deterioration in the health of the Subject that either: 
 ○ resulted in a life-threatening illness or injury, or ○ resulted in a permanent impairment of a body structure or a body function, or

	
 ○ required inpatient hospitalization or prolongation of existing hospitalization, or ○ resulted in medical or surgical intervention to prevent life threatening illness or injury or permanent impairment to a body structure or a body function. ○ led to fetal distress, fetal death or a congenital abnormality or birth defect. 
 ● Other serious important medical events. Report when the event does not fit the other outcomes, but the event may jeopardize the patient and may require medical or surgical intervention (treatment) to prevent one of the other outcomes. 
Examples of procedure related serious AEs (SAEs) may include: stiffness requiring manipulation of the hip under anesthesia, dislocation of hip requiring closed reduction, Deep Vein Thrombosis (DVT) without hospitalization. Examples of device related SAEs may include radiolucent lines around the femoral component or device dislocation.

Unexpected/Unanticipated Adverse Device Effect (UADE)	
Is defined as any serious adverse effect on health or safety, or any life-threatening problems, or death, caused by, or associated with, a device, if that effect, problem, or death was not previously identified in nature, severity, or degree of incidence in the Clinical Investigation Plan, or application, or any other unanticipated serious problem associate with a device that relates to the rights, safety, or welfare of Subjects. A UADE will not be listed in the Instructions for Use (IFU).
 
In the event of a UADE or serious adverse device effect, the Investigator should institute appropriate therapeutic and follow-up measures in accordance with good medical practice and notify the local IRB/EC. The Investigator must document follow-up treatment in the “comment” section of the AE eCRF. A full written report

	
of the event must be forwarded to DePuy Synthes within 10 working days of the discovery.
 
DePuy Synthes must notify FDA, all reviewing IRB/REB/EC's and all participating Clinical Investigators of all UADEs within 10 working days of first receiving notice of the event. In addition, the event will be reported to the DePuy Synthes Complaint Handling Unit (CHU) for investigation.

Device Deficiencies	
Are defined as in adequacy of a medical device with respect to its identity, quality, durability, reliability safety or performance. Device deficiencies include malfunctions, use errors and inadequate labeling. Device deficiencies should institute appropriate therapeutic and follow-up measures in accordance with good medical practice and notify the IRB/EC as applicable. The Investigator must document follow-up treatment of the AE and the Sponsor will report the event to the DePuy Synthes Complaint Handling Unit (CHU) for investigation.

10.4 Definition of AE Severity

An AE may be:

- **Mild:** Easily tolerated and transient in nature with minimal or no impairment of normal activity. Intervention is not indicated. Clinical or diagnostic observations only and no impairment of normal activity.
- **Moderate:** Poorly tolerated, sustained and interferes with normal activity and requires medical attention. Intervention is either noninvasive or not indicated. Activities of daily living can be sustained.
- **Severe:** Poorly tolerated, requires intervention and significantly affects activities of daily life; or places the Subject at immediate risk or harm.

10.5 Adverse Event (AE) Reporting

The definition of an AE is provided above in **Table 5**. Pre-existing medical conditions or symptoms reported prior to the surgical event are to be recorded as part of the medical history and not be recorded/reported as AEs. The only exception would be in the event there is an exacerbation of a pre-existing medical condition or symptom(s) in the post-operative time frame, then an AE must be reported.

A record of each AE, except for those anticipated AEs listed in **Exhibit L**, including details of the AEs are reported beginning from surgery and until Subject participation has ended (study completed, or consent withdrawn). Study sites have two (2) weeks from when they become aware of AEs to inform the Sponsor via the

AE CRF. If unable to enter the AE CRF you must contact the Sponsor directly or your Clinical Research Associate (CRA) to report.

AEs must be followed to resolution, or until the study completion or consent withdrawal. When a Subject ends participation in the study (either completion or consent withdrawal) AEs must be reviewed and designated, if applicable, as “resolved” and an end date provided. If AEs are not resolved at the end of a Subject’s participation, they will be considered ongoing.

An AE should be reported for each AE – meaning, if edema and bleeding occur secondary to a fall there will be two (2) AEs reported that can be attributed to a fall. Subjects should be encouraged to report AEs spontaneously and may volunteer AE information at any time. At each evaluation, the Subject should be asked if any AEs have occurred since their last evaluation. If an event occurs at an outside institution, the Investigator should attempt to obtain, if possible, required AE information.

The Investigator will record the nature, severity, treatment and outcome of the AE, and will determine their association to the device and/or the study procedure (see **Section 10.6** below).

All UADEs, SADEs and SAEs, defined in **Table 5** above, that occur during this investigation must be reported by the Investigator **no later than 72 hours** from the time when the Investigator is aware of the event via the AE CRF. If unable to enter the AE CRF you must contact the Sponsor directly or your CRA to report.

In the event of a UADE the investigator should institute appropriate therapeutic and follow-up measures in accordance with good medical practice and notify their IRB/EC. The investigator must document follow-up treatment in the “comment” section of the AE CRF. A full written report of the event must be forwarded to DePuy Synthes within 10 working days of the discovery.

DePuy Synthes must notify FDA, all reviewing IRB’s and all participating clinical investigators of all UADEs within 10 working days of first receiving notice of the event. In addition, the event will be immediately and electronically reported to the DePuy Synthes Complaint Handling Unit (CHU) for investigation.

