2 EXHIBITS

Exhibit	Details
A	Case Report Forms
B	Informed Patient Consent
C	Study Logs
D	Surgical Technique
E	Radiographic Protocol
F	Rehabilitation Protocol
G	Intentionally left blank (Monitoring Procedures maintained at Sponsor)
H	Product Labeling
I	Investigators and IRB/Ethics Committee Information
J	Statement of Investigator
K	Device Product Codes
L	Anticipated Adverse Events
M	Implant Retrieval Procedure
N	Sample Financial Disclosure Form
O	Intentionally left blank (See Section 15.0 for Publication Information)
P	References

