14 REPORTING

Reports of this study will be prepared according to the Guidance for Industry and FDA Staff: Clinical Data Presentations for Orthopaedic Device Applications.

Per the Guidance for Industry and FDA Staff- Procedures for Handling Post-Approval Studies Imposed by PMA Order

<http://www.fda.gov/downloads/MedicalDevices/DeviceRegulationandGuidance/GuidanceDocuments/ucm071013.pdf>), the applicant will provide a report to the FDA every 6 months for the first 2 years following device approval and annually thereafter until the end of the study (see **Section 16.2**).

The reports will include:

- A complete listing of all sites and IRBs.
- Enrollment updates (during enrollment) – screening/recruitment logs from all sites
- Site follow-up compliance to clinical investigation plan,
- Clinical Results- Overall Harris Hip Scores and Harris Hip sub-scores (pain, function, activity, deformity, and range of motion)
- Radiographic Results
- Safety Summary- documentation and compilation of all adverse events
- Survivorship at each year post-operatively for which there are sufficient subjects to compute survivorship

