8.7 Safety Analyses

Adverse events which occurred during subjects' participation in this PAS will be summarized. Adverse Events will be coded according to Medical Dictionary for Regulatory Activities (MedDRA) version 14.0 or higher.

An overall summary of the AE incidence will be presented, broken down by systemic and surgical site, and will include the number and percentage of subjects having one or more:

- Serious adverse event (SAE)
- Operative Site AEs
- Systemic AEs
- Device related AEs
- Procedure related AEs

The number and percent of subjects with adverse events and the 95% binomial exact confidence interval for this percent will be presented by MedDRA system organ class (SOC) and preferred term (PT) for all AEs and stratified for systemic and operative site adverse events. A subject-level listing will be provided to display details of all AEs.

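### Adverse-event (AE) tables labelled as covering all AEs omit the non-serious anticipated events that sites were told not to record, and the SAP does not say so

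*Protocol*

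**What the plan says.** **What is recorded.** Protocol 10.5 defines the AE record from surgery to the end of participation: "A record of each AE, except for those anticipated AEs listed in" Exhibit L. Protocol section 2 gives that exhibit the title "Anticipated Adverse Events"; its contents are not in the documents supplied.

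**What must still be reported.** Later in 10.5, all UADEs, SADEs and SAEs "that occur during this investigation must be reported by the Investigator" within 72 hours through the AE form. No Exhibit L exception is attached to that sentence.

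**What the reports are said to contain.**
- Protocol 10.1: "Adverse Events (AEs) must be reported for all Subjects".
- Protocol 14, on the content of reports to FDA: "Safety Summary- documentation and compilation of all adverse events".
- SAP 8.7: "Adverse events which occurred during subjects' participation in this PAS will be summarized". It then specifies the number and percentage of subjects with AEs, with an exact binomial 95% interval, by system organ class and "preferred term (PT) for all AEs and stratified for systemic and operative site adverse events", plus a subject-level listing of all AEs.
- Protocol 8.9 and the safety row of Table 1 are narrower: they promise only those AEs that were reported.

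The SAP does not mention Exhibit L or the exemption.

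**The concern.** AE type and frequency is a secondary endpoint (Protocol Table 1 and 8.7; SAP 8.4.2), and the study exists to give FDA safety and performance information on a marketed device. The collection rule leaves out a class of events; the analysis text describes a complete count. A reader of the SAP 8.7 tables has no way to know this.

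For the affected terms, a low or zero percentage with a tight interval would read as evidence that the event is rare, when it shows only that nobody was asked to record it. The same gap passes into the operative-site, systemic, device-related and procedure-related rows of the overall summary, wherever non-serious Exhibit L events fall in them.

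**Working it through.** The documents state no AE rate, so there is no planned figure to reproduce. The check compares the texts, fixes the direction of the error, and then illustrates its possible size.

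**1. Collection against analysis**

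| Event type | Recording rule (Protocol 10.5) | Implied by SAP 8.7 and Protocol 14 | Consistent? |
|---|---|---|---|
| Not in Exhibit L | Recorded | Counted | Yes |
| In Exhibit L, serious | Exempted by one sentence, required by another | Counted | Only if the 72-hour rule prevails |
| In Exhibit L, non-serious | Exempt | Counted | No |

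**2. Direction**

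Reported percentage = 100 × (subjects with at least one recorded AE) / (subjects in the Safety Analysis Set).

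The exemption can remove subjects from the numerator and removes none from the denominator. The result is therefore too low or unchanged, never too high. A subject with one exempt and one recorded AE still counts in the any-AE row; only subjects whose AEs are all exempt are lost from it. The rules on missing data do not help. SAP 8.1 bases percentages on subjects without missing data, but an event that was never requested leaves no missing value, so the subject counts as event-free. SAP 8.6 rules out imputation.

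**3. A wholly exempt term**

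Input: n = 170, the planned minimum (Protocol 8.4, SAP 7). If a preferred term lies entirely in Exhibit L, is never serious, and sites followed the exemption, then x = 0. The exact upper 95% limit is

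1 − 0.025^(1/170) = 1 − exp(−3.689/170) = 0.0215.

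The table would show 0/170, interval 0 to 2.1%, whatever the true rate.

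**4. The any-AE row, on assumptions only**

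Let p be the true any-AE percentage and s the share of those subjects whose AEs are all exempt. Neither is in the documents. Reported count = 170 × p × (1 − s), rounded to whole subjects, with an exact 95% interval:

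| Assumed p | s = 0 | s = 10% | s = 25% | s = 50% |
|---|---|---|---|---|
| 20% | 34: 20.0% (14.3–26.8) | 31: 18.2% (12.7–24.9) | 26: 15.3% (10.2–21.6) | 17: 10.0% (5.9–15.5) |
| 40% | 68: 40.0% (32.6–47.8) | 61: 35.9% (28.7–43.6) | 51: 30.0% (23.2–37.5) | 34: 20.0% (14.3–26.8) |
| 60% | 102: 60.0% (52.2–67.4) | 92: 54.1% (46.3–61.8) | 76: 44.7% (37.1–52.5) | 51: 30.0% (23.2–37.5) |

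At s = 10% every interval still covers the assumed truth. At s = 25% the interval misses it for p = 40% and 60%. At s = 50% it misses it in all three rows. The effect therefore runs from minor to decisive, and the documents do not say where in that range the study lies.

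**The case against.** The strongest reply is that this is a deliberate and ordinary scope choice. Protocol 10.1 is a general rule and 10.5 a specific exception to it. Protocol 8.9 and Table 1 speak of reported AEs, and Protocol 14 can be read in that light. In SAP 8.7 the reference to all AEs may only mean pooled as opposed to stratified tables. The endpoint is descriptive and no hypothesis is tested.

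Much of this stands. Protocol 8.9 and Table 1 do not conflict with the exemption, and 10.1 alone would be weak evidence. It does not rescue SAP 8.7, which sets out to summarise AEs that occurred and attaches confidence intervals to the result, or Protocol 14, which promises a full compilation. Neither limits itself to recorded events. The choice may be legitimate; leaving it undisclosed where the rates are tabulated is the fault.

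A reader might infer more than the documents support:
- *That all AE rates, including serious ones, are understated.* The 72-hour rule covers all SAEs, SADEs and UADEs without exception. The SAE definition in Table 5 is also broad: its examples include dislocation needing closed reduction and deep vein thrombosis without hospitalization.
- *That unanticipated device effects can no longer be judged, because their definition turns on events "not previously identified in nature, severity, or degree of incidence".* That definition concerns serious effects and problems, which remain reportable.
- *That sites applied the exemption unevenly.* Nothing in the documents shows this.

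**Conclusion.** The point holds for non-serious events listed in Exhibit L. As written, the plan labels as complete a set of AE percentages from which those events are missing by rule. The any-AE percentage, and each class or term rate that includes such events, is understated or unchanged; the exact intervals express sampling error only.

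The direction needs no knowledge of Exhibit L, but actual understatement requires that the exemption was followed. For the any-AE row, some subject's AEs must all have been exempt. For a class or term, some subject must have had an exempt event there and no recorded one.

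The size cannot be computed. The 0/170 result with an upper limit of 2.1% is exact for a wholly exempt, never-serious term at n = 170. The any-AE scenarios rest entirely on assumed rates and shares. Serious-event rates are not shown to be affected, although 10.5 leaves open which of its two rules governs a serious Exhibit L event. The primary survivorship endpoint is untouched.

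**What to change.** **In SAP 8.7:**
- Title the AE tables as excluding non-serious Exhibit L anticipated events.
- List the Exhibit L terms in a footnote, with the MedDRA preferred terms to which they map.
- Give no incidence or confidence interval for those terms, except for serious events.

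**In the final report:** state as a limitation that these events were not required to be recorded, so that the overall and class-level percentages may be too low.

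**In the protocol:** align the wording of section 14 with what is collected. Reconcile the two rules in 10.5 so that it is explicit that serious Exhibit L events are recorded.

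Removing the exemption is not the main remedy. The SAP is dated December 2023 and describes much of the conduct in the past tense, so unrecorded events probably cannot be recovered.

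The cost is wording, mapping Exhibit L to preferred terms, and a little table specification. The AE claim becomes narrower, because the report can no longer present its rates as covering all AEs.
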